4.2.2.6 Rationale for Choice of Comparator

In this study, approximately 54 subjects will be randomized in a 2:1 ratio to receive IMI/REL (Treatment Group 1) or CMS + IMI (Treatment Group 2), with ~36 subjects in Treatment Group 1 and ~18 subjects to Treatment Group 2. The sample size of Protocol 013 is small in order to minimize the duration of enrollment in this challenging study, thereby making the data on the use of IMI/REL in subjects with unmet medical need available more quickly. Given the small sample size, the number of subjects receiving a controlled comparator regimen within Protocol 013 has been limited by utilizing a disproportionate randomization scheme. Enrolling the majority of subjects to receive treatment with IMI/REL will maximize experience with IMI/REL.

Severe hospital-acquired infections due to CR Gram-negative bacteria are associated with high morbidity and mortality. The increasing incidence of CR infections and the lack of effective antibiotics have resulted in the use of colistin as a “salvage” antibiotic, essentially making colistin one of a few treatment options in critically ill patients infected with CR Gram-negative bacteria. Given its common use and relative treatment success in the target population for this current study, colistin (as CMS) is an appropriate comparator for evaluation of IMI/REL.

Although subjects infected with imipenem-resistant bacteria are the target population for this study, the combination of CMS with IMI was chosen as the comparator regimen for several reasons:

- Although colistin is commonly used in clinical practice today, the original development of colistin occurred prior to institution of the current standardized rigorous drug development procedures. As a result, there is a relative lack of pharmacological information to maximize antibacterial activity and minimize development of resistance and toxicity. Recent data suggest that the recommended dosage of colistin likely leads to suboptimal efficacy, particularly in certain patient subgroups [14, 53, 54]. Results of a recent large PK study demonstrated that, even at the maximum daily dose recommended in the package circular, it is not possible to reach adequate plasma concentrations of formed colistin, especially in patients with healthy renal function [50]. Given these results, it has been suggested that colistin might best be used as part of a highly active combination.

- In recent years, there have been worldwide reports of emergence of resistant bacteria during colistin monotherapy [63, 53, 30, 64, 65]. Combination therapy may reduce the potential outgrowth of hetero-resistant subpopulations of bacteria.
- Colistin causes an incompletely understood ‘detergent’ effect on the cell wall, resulting in increased cell permeability and potentially allowing for increased ability of other drugs to reach their antibacterial target [19]. *In vitro* studies have demonstrated a synergistic effect of colistin in combination with other antibacterial therapies, including carbapenems [66 – 68].
- Although robust controlled clinical studies are still needed to evaluate the effect of combination therapy, multiple recent studies have demonstrated improved efficacy due to combination therapy in the treatment of CR infections [12, 20, 22, 69, 70, 71].

In summary, combination therapy of colistin plus a carbapenem (such as IMI) will likely provide improved clinical success due to an expected increased bactericidal effect, and will likely limit potential toxicity by ensuring administration of maximum daily maintenance doses within the limits specified by manufacturer.

The carbapenem IMI is among the drugs of choice for treatment of severe nosocomial infections in critically ill patients [72]. Additionally, IMI is active against a wide range of Gram-positive and Gram-negative organisms, including both anaerobes and aerobes, thus providing broad-spectrum coverage. Consequently, carbapenems are often administered in clinical practice as part of a combination regimen with CMS in patients with CR infection [12, 20, 22]. Furthermore, the use of IMI in this study as the active co-comparator will allow for a straightforward evaluation of the efficacy and safety of REL as compared to colistin, as all patients in the study will receive the same β -lactam as background therapy.

4.2.3 Rationale for Endpoints

4.2.3.1 Efficacy Endpoints

For evaluation of the primary and secondary analyses, response to IMI/REL and to CMS+IMI will be based only on randomized subjects (i.e., those enrolled into Treatment Group 1 and Treatment Group 2).

The primary efficacy endpoint of the study is overall response. As the efficacy in clinical studies is typically measured differently for different infection types, overall response will be estimated based on the following: (a) all-cause mortality through Day 28 post-randomization in subjects with HABP/VABP, (b) clinical response at Day 28 post-randomization for subjects with cIAI and (c) the composite clinical and microbiological response at EFU (Day 5 to 9 following completion of therapy) for subjects with cUTI. Evaluation of the overall response will allow for a summary of REL efficacy utilizing a combination of responses that are relevant for each infection type. In addition, each of these chosen endpoints for these 3 infection types are supported in United States FDA Guidance for Industry.

There are two key secondary measurements for efficacy in this study:

- Clinical response at 28 days following initiation of IV study therapy (through Day 28 post-randomization): Evaluation of clinical response at a fixed timepoint for all subjects, regardless of infection type, will allow for comparison at a consistent timepoint across the entire study population. In addition, since the maximum duration of IV study therapy is 21 days, unless a longer duration is approved by the Sponsor, subjects will be evaluated after completion of IV study therapy, thereby allowing an assessment of clinical response at least one week following cessation of therapy in a majority of subjects.
- All-cause mortality within 28 days after initiation of study therapy (through Day 28 post-randomization): Given the severity of illness in hospitalized patients who acquire CR bacterial infections, have failed prior antibiotic treatments, and routinely require in-hospital treatment with IV antibiotics, evaluation of mortality is appropriate. A one-month mortality endpoint has commonly been used for evaluation of efficacy of antibacterial therapy against CR infections [12, 21, 23, 26].

Several additional secondary efficacy endpoints will be evaluated:

- Clinical response will be estimated at various other timepoints during the trial, including at OTX, EOT and EFU. Evaluation of clinical response at these timepoints will provide valuable data to fully characterize the response profile of the test product relative to the comparator.
- Microbiological response in subjects with cUTI will be evaluated at OTX, EOT and at EFU. Microbiological response will be measured in subjects with cUTI only since appropriate specimens (i.e., urine) can be feasibly and consistently collected at each of the endpoint visits throughout the study. Collection of lung and/or intra-abdominal specimens at all study visits may not be medically appropriate for all subjects, thus making it difficult to measure an overall microbiological response in subjects with these infections.

In addition, since there will likely be differences in clinical outcome of the various infection types being studied, as well as the potential for significant differences in duration of IV study therapy for each of these infection types, clinical response by infection type will be evaluated at EOT as an exploratory endpoint in randomized subjects. Other exploratory endpoints in this study include clinical and microbiological response by pathogen in randomized subjects, PK/PD evaluation for all subjects, and an assessment of the emergence of resistance to IMI/REL and to colistin during study therapy in randomized subjects.

Clinical response at all endpoint visits and microbiological response (cUTI) at OTX, EOT and EFU in Treatment Group 3 subjects will also be summarized as exploratory efficacy endpoints.

4.2.3.1.1 Definition of Efficacy Endpoints

4.2.3.1.1.1 Overall Response

The overall response will be estimated based on the following: (a) survival (based upon all-cause mortality) through Day 28 post-randomization in subjects with HABP/VABP, (b) clinical response at Day 28 post-randomization for subjects with cIAI and (c) the composite clinical and microbiological response at EFU for subjects with cUTI. Overall response will be determined by summarizing the proportion of subjects who survive through Day 28 post-randomization (HABP/VABP), or have a “favorable” clinical (cIAI) or “favorable” composite microbiological and clinical (cUTI) response.

A favorable response is defined differently for each infection type, and these definitions will be combined to provide an estimate of favorable overall response (See [Table 2](#) for a description of the components of the overall response). The definitions for the relevant response types that contribute to overall response are included in each of the referenced sections describing survival/all-cause mortality assessment (Section 4.2.3.1.1.1.1), clinical response (Section 4.2.3.1.1.1.2) and microbiological response (Section 4.2.3.1.1.1.3). Details regarding determination of microbiological and clinical response (“favorable” or “unfavorable”) in support of evaluation of overall response at Day 28 post-randomization are provided in Section 8.2.

Table 2 Description of Individual Infection Site Responses Supporting Determination of Favorable Overall Response (Primary Endpoint)

Infection Site	Type of Response (Timing)	Favorable Response	Reference (Section/Table #) for Definition of Response
HABP/VABP	Survival/All-Cause Mortality (Day 28)	Survival at Day 28	Section 4.2.3.1.1.1.1
cIAI	Clinical Response (Day 28)	
 • Sustained cure • Cure 	Section 4.2.3.1.1.1.2 Table 5
cUTI	Composite Clinical (EFU) and Microbiological Response (EFU)	Clinical Response: 
 • Sustained cure • Cure Microbiological Response: 
 • Sustained eradication 	Clinical Response: Section 4.2.3.1.1.1.2 Table 5 Microbiological Response: Section 4.2.3.1.1.1.3 Table 8

4.2.3.1.1.1.1 Survival/All-Cause Mortality

Survival status (i.e., whether the subject is alive or dead) at Day 28 will be evaluated for all subjects. In support of the primary objective of overall response, survival will be specifically determined in subjects with HABP/VABP. In addition, the key secondary efficacy endpoint will be based on an all-cause mortality evaluation in all subjects, regardless of primary infection site, at Day 28 following randomization.

4.2.3.1.1.1.2 Clinical Response

In support of evaluation of both the primary endpoint (i.e., overall response), as well as secondary and exploratory endpoints for the study, efficacy assessments will include evaluation of clinical response. Clinical response will be assessed for all subjects based on evaluation by the investigator at the OTX, EOT, EFU and Day 28 post-randomization visits. Based on comparison to baseline clinical signs and symptoms of the subject's infection(s), the investigator will determine the clinical response rating (and record the response on the appropriate eCRF) at each visit as described in [Table 3](#) (for OTX visit), [Table 4](#) (for EOT visit) and [Table 5](#) (for EFU and Day 28 visits).

In support of evaluation of efficacy endpoints that include clinical response (i.e., overall response and clinical response), the clinical response rating determined by the investigator at each visit will be categorized as "favorable" or "unfavorable". Details regarding determination of the category of clinical response ("favorable" or "unfavorable") in support of relevant study endpoints are provided in the tables describing clinical response as well as Section 8.2.

Table 3 Definitions of the Clinical Response Rating at the OTX Visit (Day 3)

Clinical Response ^a	Response Definition
Improved	All or most pretherapy signs and symptoms ^b of the index infection(s) have improved or resolved (or returned to "preinfection status") AND , for cIAI subjects, no unplanned surgical procedures or percutaneous drainage procedures have been performed.
Persistence	Little apparent response to IV study therapy in prestudy signs and symptoms ^b of the index infection(s): persistence of most or all pretherapy signs and symptoms.
Progression	No apparent response to IV study therapy in prestudy signs and symptoms ^b of the index infection(s): progression/worsening of most or all pretherapy signs and symptoms.
Indeterminate	Study data are not available for evaluation of clinical response for any reasons at the OTX visit, including: a) Complication related to underlying medical condition; OR b) Subject was withdrawn for any reason before sufficient data had been obtained to permit evaluation for any reason; OR c) Extenuating circumstances preclude classification as "improved," "persistence," or "progression;" OR d) Death occurred during the study period and the index infection was clearly noncontributory.
^a A favorable clinical response at OTX requires an assessment of "improved". ^b Refer to Table 13 for a description of disease-specific clinical signs and symptoms.	

Table 4 Definitions of the Clinical Response Rating at the EOT Visit

Clinical Response ^a	Response Definition
Cure	All pretherapy signs and symptoms ^b of the index infection(s) have resolved (or returned to "preinfection status") AND no additional IV antibiotic therapy is required, AND , for cIAI subjects, no unplanned surgical procedures or percutaneous drainage procedures have been performed.
Improved	All or most pretherapy signs and symptoms ^b of the index infection(s) have improved or resolved (or returned to "preinfection status") AND no additional IV antibiotic therapy is required, AND , for cIAI subjects, no unplanned surgical procedures or percutaneous drainage procedures have been performed.
Failure	No apparent response to IV study therapy in prestudy signs and symptoms ^b of the index infection(s): persistence or progression of most or all pretherapy signs and symptoms.
Indeterminate	Study data are not available for evaluation of clinical response for any reasons at the EOT visit, including: a) Complication related to underlying medical condition; OR b) Subject was withdrawn for any reason before sufficient data had been obtained to permit evaluation for any reason; OR c) Extenuating circumstances preclude classification as "cure," "improved," or "failure;" OR d) Death occurred during the study period and the index infection was clearly noncontributory.
^a A favorable clinical response at EOT requires an assessment of "cure" or "improved". ^b Refer to Table 13 for a description of disease-specific clinical signs and symptoms.	

Table 5 Definitions of the Clinical Response Rating at the EFU and Day 28 Post-Randomization Visit

Clinical Response ^a	Response Definition
Sustained Cure	All pretherapy signs and symptoms ^b of the index infection(s) have resolved (or returned to "preinfection status") with no evidence of resurgence AND no additional antibiotic therapy (beyond IV study therapy) was required, AND , for cIAI subjects, no unplanned surgical procedures or percutaneous drainage procedures have been performed.
Cure	All pretherapy signs and symptoms ^b of the index infection(s) have resolved (or returned to "preinfection status") AND no additional IV antibiotic therapy is required, AND , for cIAI subjects, no unplanned surgical procedures or percutaneous drainage procedures have been performed.
Failure	No apparent or insufficient response to IV study therapy in prestudy signs and symptoms of the index infection(s): persistence, progression, or improvement (without full resolution) of all pretherapy signs and symptoms ^c
Relapse	Subjects with a favorable clinical response (cure or improved) at the EOT visit have worsening signs and symptoms ^b of the index infection(s) by the EFU or Day 28 post-therapy visit.
Indeterminate	Study data are not available for evaluation of efficacy for any reasons, including: a) Complication related to underlying medical condition; OR b) Subject was withdrawn for any reason before sufficient data had been obtained to permit evaluation of clinical response; OR c) Extenuating circumstances preclude classification as "sustained cure," "failure," or "relapse;" OR d) Death occurred during the study period and the index infection was clearly noncontributory.
^a A favorable clinical response at EFU or Day 28 post-randomization requires an assessment of "cure" or "sustained cure". To be considered "sustained cure", the clinical response for the prior visit must have been considered "cure". A clinical response of "cure" is only relevant at EFU for subjects with a response of "improved" at EOT. ^b Refer to Table 13 for a description of disease-specific clinical signs and symptoms.	

4.2.3.1.1.3 Microbiological Response

In addition to clinical response assessments, subjects with cUTI will be evaluated for microbiological response. Microbiological response will be evaluated separately for each qualifying baseline uropathogen. For randomized subjects, a qualifying pathogen is defined as any Gram-negative baseline pathogens that are imipenem-resistant, IMI/REL-susceptible, and colistin-susceptible. For subjects enrolled in Treatment Group 3, a qualifying pathogen is defined as any Gram-negative baseline pathogens that are imipenem-resistant and colistin-resistant, but IMI/REL-susceptible. The by-pathogen response rating will be determined by the Sponsor. The by-pathogen microbiological response rating will be determined at the OTX, EOT, and EFU visits based on local laboratory results (per eCRF data provided by the investigator) from urine cultures collected at each of these visits relative to the pathogen(s) isolated at baseline/admission, as described in [Table 6](#) (for the OTX visit), [Table 7](#) (for the EOT visit) and [Table 8](#) (for the EFU visit). Of note, microbiological samples are not collected at the Day 28 post-randomization visit.

Antibiotic susceptibility results as well as microbiological response will be summarized by qualifying pathogen. In support of evaluation of efficacy endpoints that include microbiological response (i.e., microbiological response and overall response), the by-pathogen microbiological response rating will be utilized to categorize the overall microbiological response (i.e., overall microbiological response for the subject based on the response of all qualifying uropathogens present in the baseline culture) as “favorable” or “unfavorable.” For subjects from whom only one qualifying pathogen is isolated, the overall microbiological response assessment will be based on the microbiological response rating for that pathogen. For subjects from whom more than one qualifying baseline pathogen is isolated, the overall microbiological response outcome will be based on microbiological culture results for all qualifying baseline pathogens.

Details regarding determination of the category of overall microbiological response outcome (“favorable” or “unfavorable”) in support of relevant study endpoints are provided in the tables describing microbiological response as well as in Section 8.2.

Table 6 Definitions of the By-Pathogen Microbiological Response Rating at the OTX Visit (Day 3)

Microbiological Response ^{a,b,c}	Response Definition
Eradication	A urine culture taken at the OTX visit shows eradication of the uropathogen (e.g., $\geq 10^5$ CFU/mL is reduced to $< 10^4$ CFU/mL) found at study entry.
Persistence ^d	A urine culture taken at the OTX visit grows a uropathogen (at $\geq 10^4$ CFU/mL) found at study entry.
Superinfection	A urine culture at the OTX visit grows a uropathogen (at $\geq 10^5$ CFU/mL) other than a baseline pathogen during the course of IV study therapy OR emergence during IV study therapy of a new pathogen at a distant (non-urine), sterile site along with worsening signs and symptoms of infection.
Indeterminate	a) Follow-up urine culture is not available at the OTX visit due to subject death or withdrawal from study; OR b) Microbiological data are incomplete; OR c) Assessment not possible due to protocol violation; OR d) Any other circumstance which makes it impossible to define the microbiological response
^a A microbiological response rating will be determined separately for each qualifying pathogen isolated at baseline. ^b If a new/emergent pathogen is identified after initiation of IV therapy which was not identified at baseline, regardless of susceptibility profile, the microbiological response rating for the new pathogen will be considered “superinfection”. ^c A favorable overall microbiological response at OTX requires “eradication” of all baseline pathogens. ^d If a subject is discontinued from IV study therapy due to clinical failure (i.e., unfavorable clinical response), but persistence of the admission pathogen is not confirmed by culture results or no culture is obtained at the time of clinical failure, the admission pathogen will be presumed to have persisted.	

Table 7 Definitions of the By-Pathogen Microbiological Response Rating at the EOT Visit

Microbiological Response ^{a,b,c}	Response Definition
Sustained eradication ^d	A urine culture taken at the EOT visit ^c still shows eradication of the uropathogen (e.g., $\geq 10^5$ CFU/mL is reduced to $< 10^4$ CFU/mL) found at study entry.
Eradication ^e	A urine culture taken at the EOT visit ^c shows eradication of the uropathogen (e.g., $\geq 10^5$ CFU/mL is reduced to $< 10^4$ CFU/mL) found at study entry.
Persistence ^f	A urine culture taken at the EOT visit ^g grows a uropathogen (at $\geq 10^4$ CFU/mL) found at study entry.
Superinfection	An infection-site culture grows a uropathogen (at $\geq 10^5$ CFU/mL) other than a baseline pathogen during the course of IV study therapy OR emergence during IV study therapy of a new pathogen at a distant (non-urine), sterile site along with worsening signs and symptoms of infection.
Indeterminate	a) Follow-up urine culture is not available at the EOT visit ^c due to subject death or withdrawal from study; OR b) Microbiological data are incomplete; OR c) Assessment not possible due to protocol violation; OR d) Any other circumstance which makes it impossible to define the microbiological response
^a A microbiological response rating will be determined separately for each qualifying pathogen isolated at baseline. ^b If a new/emergent pathogen is identified after initiation of IV therapy which was not identified at baseline, regardless of susceptibility profile, the microbiological response rating for the new pathogen will be considered “superinfection”. ^c A favorable overall microbiological response at EOT requires “eradication” or “sustained eradication” of all baseline pathogens. ^d A microbiological response of “sustained eradication” at EOT is used when the microbiological response assessment at OTX visit was also “eradication”. ^e A microbiological response of “eradication” at EOT is used when this is the first time that microbiological response assessment is “eradication (i.e., OTX visit microbiological response assessment was not “eradication”). ^f If a subject is discontinued from IV study therapy due to clinical failure (i.e., unfavorable clinical response), but persistence of the admission pathogen is not confirmed by culture results or no culture is obtained at the time of clinical failure, the admission pathogen will be presumed to have persisted. ^g If a culture is not available at EOT, an assessment at this visit can be made from the last available urine culture which was collected after at least 48 hours of IV study therapy.	

Table 8 Definitions of the By-Pathogen Microbiological Response at the EFU Visit

Microbiological Response ^{a,b,c}	Response Definition
Sustained eradication ^d	A urine culture taken at the EFU visit still shows eradication of the uropathogen (e.g., $\geq 10^5$ CFU/mL is reduced to $< 10^4$ CFU/mL) found at study entry.
Persistence	A urine culture taken at the EFU visit grows a uropathogen (at $\geq 10^4$ CFU/mL) found at study entry.
New Infection	A uropathogen, other than a microorganism found at baseline is present in the urine (at a level $\geq 10^5$ CFU/mL) any time after IV study therapy is finished; OR A pathogen is isolated from a distant (non-urine), sterile after IV study therapy has been completed.
Recurrence	A urine grows a uropathogen (at a level $\geq 10^5$ CFU/mL) taken any time after documented eradication.
Indeterminate	a) Follow-up urine culture is not available at the EFU visit due to subject death or withdrawal from study; OR b) Microbiological data are incomplete; OR c) Assessment not possible due to protocol violation; OR d) Any other circumstance which makes it impossible to define the microbiological response
^a A microbiological response rating will be determined separately for each qualifying pathogen isolated at baseline. ^b If a new/emergent pathogen is identified after EOT which was not identified at baseline, regardless of susceptibility profile, the microbiological response rating for the new pathogen will be considered “new infection”. ^c A favorable overall microbiological response at EFU visit requires “sustained eradication” of all baseline pathogens. ^d A microbiological response of “sustained eradication” at EFU is used when the microbiological response assessment at EOT visit is also “eradication”.	

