5.5 Concomitant Medications/Vaccinations (allowed & prohibited)

Medications or vaccinations specifically prohibited in the exclusion criteria are not allowed during the ongoing trial. Listed below are some specific restrictions for concomitant therapy or vaccination during the course of the trial. If there is a clinical indication for one of these or other medications or vaccinations specifically prohibited during the trial, discontinuation from trial therapy or vaccination may be required. The investigator should discuss any questions regarding this with the Sponsor Clinical Director. The final decision on any supportive therapy or vaccination rests with the investigator and/or the subject's primary physician. However, the decision to continue the subject on trial therapy or vaccination schedule requires the mutual agreement of the investigator, the Sponsor and the subject.

NOTE: With the exception of >24 hours of colistin for subjects in Treatment Groups 1 and 2 (see Section 5.1.3.1, Criterion #4) there are no restrictions to prior antimicrobial therapy.

The following concomitant medications/therapies are NOT permitted in this study:

1. Valproic acid/divalproex sodium
2. Non-study IV, oral, or inhaled antibacterial treatments with known coverage of Gram-negative bacteria of interest (i.e., Enterobacteriaceae, *Pseudomonas* spp. and Gram-negative anaerobic bacilli).

Importantly, the following antibacterial medications are permitted:

- a. IV vancomycin, IV daptomycin, or IV linezolid to treat confirmed or suspected MRSA infection. If added, IV vancomycin, daptomycin, or linezolid should be used according to the investigator's usual practice. Daptomycin is not indicated for the treatment of HABP/VABP.

- b. IV linezolid or IV daptomycin to treat confirmed or suspected VRE infection. If added, linezolid or daptomycin should be used according to the investigator's usual practice. Daptomycin should not be used to treat HABP/VABP.
 - c. TMP/SMX or other standard-of-care agent for prophylaxis of opportunistic infection (e.g., *P. jiroveci* infection) in immunocompromised subjects.
3. Use of systemic antifungal therapy for disseminated fungal infection, fungemia, or for pulmonary infection in HABP/VABP subjects.

Antifungal medications are permitted in the following clinical situations:

- a. Antifungal medications for treatment of mucocutaneous infection (e.g., vaginal candidiasis, onychomycosis).

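### Table 5 sets different antibiotic conditions for its two favourable ratings, so at EFU the same oral course is favourable for a subject improved at EOT but not for one already cured

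*Combined protocol and SAP*

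**What the plan says.** Table 5 gives the investigator's clinical ratings at EFU and Day 28. Footnote a counts *cure* and *sustained cure* as favourable. Their antibiotic conditions differ:

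- *Sustained cure*: "no additional antibiotic therapy (beyond IV study therapy) was required". This covers any route.
- *Cure*: "no additional IV antibiotic therapy is required". Oral therapy is not mentioned.

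Footnote a also decides who can receive which rating. *Sustained cure* needs a rating of *cure* at the previous visit. For the other row it says: "A clinical response of 'cure' is only relevant at EFU for subjects with a response of 'improved' at EOT".

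In Table 4 (EOT), the *cure* and *improved* rows share the IV-only condition, so an oral antibiotic does not alter the EOT rating.

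Table 2 takes the Table 5 rating at EFU, together with microbiological response, as the cUTI part of the primary endpoint, and the Table 5 rating at Day 28 as the cIAI part. Day 28 clinical response in all subjects is a key secondary endpoint, and EFU clinical response is a further secondary endpoint.

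Section 5.5 lists as not permitted "Non-study IV, oral, or inhaled antibacterial treatments with known coverage of Gram-negative bacteria of interest". It allows certain other antibacterials, including prophylaxis in immunocompromised subjects. It does not say how either kind of use is scored in Table 5.

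**The concern.** Two ratings that count equally as success should not carry different conditions on the same post-treatment event when subjects are assigned to them by speed of response. As written, the stricter condition falls on the subject who had resolved by EOT and the looser one on the subject who had only improved. Footnote a also closes the way back: a subject who misses *sustained cure* because of an antibiotic cannot drop to *cure* at EFU.

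This is an estimation trial without efficacy tests, so the response proportions are the result. With planned strata of 10 and 5, the rating of a single subject is visible in the reported rate.

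**Working it through.** The plan gives no figure for this point, so the check applies the definitions to worked cases and then sizes one reclassification.

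**1. Cases at EFU.** Every subject completed IV therapy, is fully resolved at EFU, and had no further IV antibiotic and no unplanned procedure. They differ in EOT rating and in whether an oral non-study antibiotic was taken after EOT.

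| EOT rating | Oral antibiotic | *Sustained cure* | *Cure* | EFU result |
|---|---|---|---|---|
| cure | no | met | closed by footnote a | favourable |
| improved | no | closed (prior visit not cure) | met | favourable |
| cure | yes | fails antibiotic condition | closed by footnote a | no favourable rating |
| improved | yes | closed (prior visit not cure) | met (IV-only condition) | favourable |

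In the third row *failure* does not fit, because it needs incomplete resolution. *Relapse* does not fit, because it needs worsening. That leaves *indeterminate*, which is not favourable. The wording of that row does not list *cure* among the ratings that could not be assigned.

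**2. The same subjects at Day 28, still resolved.** Without an oral antibiotic both reach *sustained cure*. This takes *sustained cure* at EFU as satisfying the prior-visit requirement, which footnote a does not actually say. With the oral antibiotic the result depends on how footnote a is read:

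| Reading of footnote a | Cure at EOT | Improved at EOT |
|---|---|---|
| A. *Cure* exists only at EFU | not favourable | not favourable |
| B. The restriction applies at EFU only; *cure* is open to all at Day 28 | favourable | favourable |
| C. *Cure* is for subjects improved at EOT, at either visit | not favourable | favourable |

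Only reading C repeats the EFU asymmetry, and the text does not choose among the three.

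**3. Other rules that might settle it.** The failure rule in Section 8.2.5.1 covers subjects who stop IV therapy for lack of efficacy; these subjects completed it. Section 5.5 restricts certain drugs but gives no scoring rule.

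**4. Size of one reclassification.** The planned mMITT sizes in Section 8.2.7 are 10 and 5 per infection type and 30 and 15 overall (Groups 1 and 2). The change in a rate is 1/n:

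- Stratum: 1/10 = 10 points; 1/5 = 20 points.
- Pooled: 1/30 = 3.3 points; 1/15 = 6.7 points.

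The intervals use the Agresti-Coull formula: ñ = n + z², p̃ = (x + z²/2)/ñ, limits p̃ ± z√(p̃(1 − p̃)/ñ), with z = 1.96. For 8/10, ñ = 13.84 and p̃ = 9.92/13.84 = 0.717, giving 47.9 to 95.4, as in Table 18.

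| Group | Before | After one subject moves |
|---|---|---|
| Group 1 stratum | 8/10 = 80.0% (47.9, 95.4) | 7/10 = 70.0% (39.2, 89.7) |
| Group 2 stratum | 4/5 = 80.0% (36.0, 98.0) | 3/5 = 60.0% (22.9, 88.4) |
| Group 1 pooled | 24/30 = 80.0% (62.3, 90.9) | 23/30 = 76.7% (58.8, 88.5) |
| Group 2 pooled | 12/15 = 80.0% (54.0, 93.7) | 11/15 = 73.3% (47.6, 89.5) |

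The starting rate of 80% is illustrative; it is one of the scenarios in Table 18.

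**The case against.** The strongest reply is that the affected group is narrow. Stopping IV therapy for lack of efficacy, worsening after a favourable EOT, and incomplete resolution are all unfavourable already. What remains is a subject who completed IV therapy, did not worsen, resolved fully and still took an oral antibiotic. No oral step-down is described and no frequency is given. In cUTI a favourable composite also needs sustained eradication. Ratings are blinded, and nothing indicates a bias between arms. All of this stands, and it limits the expected effect. It does not supply a rating for the subject left without one.

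Section 5.5 cuts both ways. Its text refers to the trial, while exclusion criterion 10 refers to the course of study therapy, so its reach after EOT is unclear. If it applies after EOT, the oral course is a deviation and the per-protocol analysis may exclude the subject, but the primary mMITT analysis still has to score it. If it does not apply, the course is not a prohibited one.

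A reader might infer three stronger points that the documents do not support:

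- *That Table 5 generally counts rescue as success, or credits study drug with prohibited treatment.* The existing unfavourable rules catch most rescue, and whether the ban extends past EOT is unsettled.
- *That the ratings cannot be repaired in analysis.* Concomitant medications, signs and symptoms are recorded at these visits, and medical review precedes unblinding. What is missing is a prespecified rule.
- *That any added antibiotic must be rated failure.* That would conflict with the current *failure* row, and a single IV-only condition would also remove the asymmetry.

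**Conclusion.** The inconsistency is real and unambiguous at EFU. It reaches the clinical half of the primary endpoint in the cUTI stratum, 15 of 45 planned mMITT subjects, and the secondary EFU clinical response in all subjects. Those 15 are the subjects exposed to the rule, not the number expected to change.

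A reader might extend the reversal to Day 28, and so to the cIAI primary component and the key secondary endpoint. The documents do not support that: the asymmetry appears under one of three readings of footnote a. The correct statement is that Day 28 scoring of these subjects is undefined, which is itself worth correcting because a primary component depends on it.

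The 10- and 20-point shifts are per subject and assume the planned stratum sizes are reached. How many subjects would be affected cannot be estimated from the documents, and no direction of effect between arms is claimed.

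**What to change.** Before unblinding:

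1. Put one identical antibiotic condition in both favourable rows of Table 5. Limit it to systemic antibacterials given for the index infection, and do not count agents that Section 5.5 permits for other purposes. Otherwise permitted prophylaxis could, read literally, block *sustained cure*.
2. State which category a subject who does not meet the condition receives, whatever the EOT rating. If that category is *failure*, its definition must be amended to match.
3. Amend footnote a to say how *cure* and *sustained cure* apply at Day 28, including whether *sustained cure* at EFU satisfies the prior-visit requirement.
4. Reconcile the rule with Section 5.5 and exclusion criterion 10, so that it is clear which period after EOT they cover.
5. Report the condition not chosen (IV-only or any-route) as a sensitivity analysis derived from the recorded concomitant medications.

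Table 4 needs no change, since its two favourable rows already agree. The cost is a small change to protocol wording and eCRF instructions, plus one derived analysis. If the any-route condition is chosen, the favourable rate may be slightly lower.
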